Participants will be screened for COVID-19 upon arrival to the clinic. A bilateral ear exam will then be performed. A pregnancy test will be performed for all female participants of childbearing age. The MDS-UPDRS part III and the Timed Up and Go (TUG) will then be administered. Participants will then undergo the Magnetic Resonance Imaging (MRI) protocol (see below) and the transcranial Doppler sonography recordings of a hypercapnia challenge. Pulse wave velocity may be measured at this time.

After the collection of baseline neuroimaging data, participants will return to the clinic where they and their caregivers will try on an unpowered Device, will be randomized and trained on the use and care of the tvCVS Device. The Device will be allocated to the participant and the coordinator should note the Device ID in the Device Inventory Control Log. The study coordinator will assist the participant in adjustment of the headset settings. See Clinical Coordinator Quick Reference Guide for procedures. Once the participant confirms that the headset is comfortable enough to proceed, the participant will be randomized by selecting an envelope with printed bar code from the pack of four. Note that a given pack of 4 should be completed before a new pack is opened. The study coordinator will load the prescription on the Device and then place the unopened envelope in the study binder. * Envelopes should be only be opened under circumstances where treatment allocation must be known for management of an adverse event. Once the Participant has demonstrated proficiency in Device care and use procedures, they will take their designated Device home and will self-administer treatments twice daily during the treatment period. Participants will also be provided with a detailed handout (step-by-step guide with pictures), for self-administration of device treatments. Coordinators will also call the participant the next day to confirm that the participant was able to

administer treatments. If necessary, additional training sessions via telemedicine may be scheduled.

MRI protocol:

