After the completion of the MRI scan, the coordinator will accompany the study participant to the clinic for TCD recordings. There, the participant will receive a second hypercapnia challenge (using the same conditions described above) while undergoing TCD recording. Pulse wave velocity (PWV) may be measured at this time.

Treatment period:

All participants will treat twice daily, at least one hour apart. Each treatment duration is 19 minutes 39 seconds. Participants will only wear the device when administering a treatment per protocol. The treatment period is anticipated to last for 12 weeks. However, treatment may be

extended for approximately 2 additional weeks in the case of scheduling conflicts (such as those imposed by standard operating procedures imposed by WFU to limit the spread of COVID-19). Patients should continue to treat twice daily up until the time of the end of treatment clinic visit.

Interim phone calls:

- Participants will be called the next day after their Device training visit to confirm that participants were able to successfully administer treatment in the home setting.
- Scheduled follow up phone calls will be made at week 3, week 6 and week 9. During these calls, the coordinator will ask about any adverse events, any changes to concomitant medications and to confirm no issues have arisen with use of the Device.
- Participants will also have received the contact information for the site coordinator so that they may report potential adverse events or issues with the Device in real time.

End of treatment visit (remote) – week 12:

During this remote visit, the study coordinator will administer the NMSS, the MDS-UPDRS parts II and IV as well as the modified MDS-UPDRS part III. They will also administer the MoCA, the MRI safety screening as well as a Device usability questionnaire. Participants will then be asked to completed the (PROs) including the Geriatric Depression Scale (GDS), the Parkinson's Anxiety Scale (PAS), the Epworth Sleepiness Scale (ESS), the Functional Assessment of Chronic Illness Therapy – Fatigue (FACIT-F) and the Device Usability Questionnaire and to bring them to their scheduled imaging visit. Participants will also be told to bring their Devices with them to the next clinic but that they should continue with twice daily treatments until their imaging visit.

End of treatment visit (in clinic)- week 12, 1 day after remote visit:

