For treatment, all participants will recline on a 22° wedge pillow (provided by Scion) to position the horizontal semicircular canal in the optimal orientation for maximal caloric effect. Participants will start and stop the device with a single push button to activate a run. Starting and stopping the device requires an extended push (2 seconds) to avoid false activations due to short button pushes. The OLED display provides a “countdown” icon to provide the subject with feedback on how the treatment session is proceeding. The display also tells the subject how many treatments are left within the prescription period. The device provides an audio alert that denotes the start and completion of a treatment run. The same visual and auditory information will be presented for both neurostimulation patterns.

Device treatment does not require active engagement of the subject. Therefore, participants will be told that they should feel free to read, watch television or rest so long as they remain in the supine position for the duration of treatment.

For the stimulation 1 treatment, time-varying saw-tooth waveforms (shown in Figure 2C) are delivered. The waveform schedule for active treatment participants will consist of a warm sawtooth delivered to one ear and a cold sawtooth delivered to the other ear (see Figure 1C for an example). The warm sawtooth will go from body temperature to 42 °C, and the cold sawtooth will go from body temperature to 17 °C. The two waveforms will be delivered simultaneously but will have different oscillation frequencies. After each 2-day period, the warm and cold waveforms will be switched so that the opposite ears will receive the different caloric stimulation. Thus, every 2 days, the ear receiving the cold stimulus will be switched to the warm stimulus and vice versa. This protocol will be followed for 84 days. Additional window days will be available to accommodate for potential scheduling conflicts.

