Sponsor, the Unblinding investigator may open the randomization envelope to obtain the treatment allocation. The safety event will be reported as required by this protocol. Should treatment allocation information be required for handling of an AE, a CRF providing the details of the incident will be completed.

Analysis of all study endpoints will be completed by individuals blinded to treatment allocation. The participants will be told, within the informed consent document that they may not directly benefit from taking part in the study. Participants will be told that the device stimulates the brainstem but will NOT be told that the device provides caloric vestibular stimulation (CVS) or that the device works by modulating temperature of the ear probes.

The study team will work to develop a culture of collaboration and mutual respect with the study participants. Participants will be told that their participation in the trial and adherence to the study protocol will help to develop a potential new treatment for PD patients. Participants will also be reminded that the success of the study is dependent on their willingness to participate in a blinded fashion, and should they be tempted to try to investigate more about the device during the clinical trial, engagement in these activities are likely to corrupt the integrity of the study results. Participants will be offered the opportunity to learn about their stimulation condition after the completion of the study.

Site personnel should encourage study participant adherence to Device usage throughout duration of the trial but maintain a neutral position regarding efficacy to promote scientific integrity of the study.

Study Intervention Adherence:

The actual, measured temperature profile for each run will be saved to Device memory, as will the time and date of each treatment run. A team at Robling will download the Device adherence and temperature recording data via a USB port that is covered by a hatch on the device body. They will provide treatment adherence data to the study coordinator and the raw files which can be evaluated to confirm treatment allocation will be saved in a central repository and shared with Scion NeuroStim after study database lock.

Discontinuation of Study Intervention:

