AEs will be summarized by the Device sponsor CRA. Device sponsor management and the site PI will regularly convene to monitor and review AE reports. All AEs will be evaluated on an individual basis to determine whether the occurrence may be related to device use. Should a serious adverse event (SAE) occur that is deemed to be likely related to device use, the potential for the universality will be assessed within 48 hours. If evidence suggests that treatments with the device could create a safety concern for participants, the study Device sponsor will be pause or stop the study early, as appropriate.

It should be noted that the above scenario is considered to be highly unlikely. The device has been designated as NSR by the FDA, and there were no reports of significant or unexpected AEs

that were potentially related to device in either the PD single-site RCT or the episodic migraine RCT.

Participant Discontinuation/Withdrawal from the Study:

Withdrawal Criteria

Study participants must be withdrawn from the clinical trial if any of the following events occur:

- the participant is significantly and willfully non-adherent to the requirements of the protocol (principal investigator & Device Sponsor decision),
- the participant develops an illness (adverse event) that would interfere with his/her continued participation,
- the participant withdraws his/her consent,
- the principal investigator feels that it is the participant's best interest to be withdrawn,
- SNS discontinues the study or has achieved the targeted enrollment

If the study participant is discontinued from the participation in the study for any reason, the principal investigator must make every effort to perform all evaluations for the final visit, collect the device from the participant (if it is still within their possession) and document the reasons for discontinuation. If the participant withdraws from the study due to an adverse event that is potentially related to use of the device, the coordinator should continue to follow up with the participant at regular intervals, and at least every two weeks until the AE resolves or until the participant withdraws consent for the follow-up procedure. Reasons for study withdrawal should be documented on the subject disposition form.

Lost to Follow-up

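### No objective record of Device use is planned to reach the site during the 12 weeks, and the week 3, 6 and 9 calls do not ask about sessions done, so low use may go unnoticed while it could still be raised

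*Combined protocol and SAP*

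**What the plan says.** All references are to the combined protocol and SAP.

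- **Interim phone calls.** There is one early check of use: "Participants will be called the next day after their Device training visit to confirm that participants were able to successfully administer treatment". At weeks 3, 6 and 9, "the coordinator will ask about any adverse events, any changes to concomitant medications and to confirm no issues have arisen" with Device use. Participants also hold contact details for reporting problems at any time.
- **Study Intervention Adherence.** The Device stores the temperature profile of every run, "as will the time and date of each treatment run". The log is then read out: "A team at Robling will download the Device adherence and temperature recording data via a USB port". Robling passes adherence data to the study coordinator; no date is given. Site staff are to encourage use throughout the trial while staying neutral on efficacy.
- **End of treatment visit (in clinic), week 12.** The Device is collected here and then sent to Robling.
- **Description of Study Intervention.** "The display also tells the subject how many treatments are left within the prescription period". Visual and auditory information is stated to be the same for both stimulation patterns.
- **Baseline imaging / Device training visit.** "If necessary, additional training sessions via telemedicine may be scheduled".
- **Withdrawal Criteria.** One ground is that "the participant is significantly and willfully non-adherent to the requirements of the protocol", decided by the principal investigator and the Device sponsor. No numeric threshold is given.

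**The concern.** Exposure is unsupervised, and the protocol asks staff to encourage it, yet no routine step shows staff how much treatment a participant is taking until the Device has gone back. A question about problems with the Device does not fill the gap: someone whose Device works but who treats once a day can truthfully report no problem. Spontaneous reports may also be less likely, because under Randomization, Blinding and Unblinding participants are told not to discuss their treatment experience with study staff unless there is pain.

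What is at stake is dilution. Missed sessions in the stimulation 1 arm would tend to pull both primary contrasts (perfusion and cerebrovascular reactivity) towards no difference, and a trial of up to 20 has little room to absorb that. The log will describe low use afterwards, but by then it cannot be raised.

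**Working it through.** **Timing, from the text.** The log is read only by USB, by a team at Robling. The only routine transfer to Robling follows collection at week 12. No remote transmission or interim download is described. It follows that no objective count is planned to reach the site during treatment. This is an inference from two sections; no sentence says the download happens only then, and a failed Device or an early withdrawal could bring one back sooner. In the Schedule of Activities (partly broken in the text available), the nearest row to an adherence check is confirmation of the first home treatment.

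**Sessions due.** Twice daily for 84 days: 2 × 84 = 168. Due by week 3: 2 × 21 = 42; by week 6: 2 × 42 = 84; by week 9: 2 × 63 = 126. If treatment is extended by two weeks, the total is 2 × 98 = 196.

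**Why the starting count matters.** The documents allow window days and do not give the prescription length loaded on the Device. If the counter starts at 168, a participant on schedule shows 126, 84 and 42 left at the three calls. If it starts at 196, the same participant shows 154, 112 and 70. Judging the second against the first would make a fully adherent participant look 28 sessions behind.

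**Scale of missed use.** Background, Rationale and Context reports 84 ± 5% adherence in both groups of the earlier 8-week trial. Applied to 168 sessions: 0.84 × 168 ≈ 141 done and 27 missed. At 79% it is about 133 and 35; at 89%, about 150 and 18.

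**Illustration of dilution.** The plan gives no effect size, SD, alpha or power, so there is no figure to reproduce. Assumed: 10 per arm, two-sided 5%, two-sample t-test, a standardized effect d at full use, and an effect proportional to the share of sessions taken, a. Power is the probability that a noncentral t on 18 degrees of freedom, with noncentrality a × d × √(10/2), exceeds 2.101 in absolute value. For d = 1.3 and a = 0.84, noncentrality is 0.84 × 1.3 × 2.236 = 2.44 and power is 64%.

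| Mean use | d = 1.3 | d = 1.0 |
|---|---|---|
| 100% | 78% | 56% |
| 95% | 74% | 52% |
| 90% | 70% | 48% |
| 84% | 64% | 43% |
| 70% | 49% | 32% |

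The table shows how power falls with use under those assumptions. It does not show what the calls would gain, because nothing in the documents says how far asking for a count raises use.

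**The case against.** A reader might infer that low use cannot be corrected at all. The documents do not support that. The day-after call, optional telemedicine retraining, the Device question at three calls, the open contact route and general encouragement all allow some correction. Data and Safety Monitoring also lists adherence to the treatment plan as a monitoring focus, though without a data source. What is missing is a measured trigger.

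A reader might also infer that the withdrawal criterion operates without data. That too goes further than the text. The criterion covers all protocol requirements, so missed visits, medication changes and self-report can inform it. It also requires wilful conduct, which a session count cannot show. What can be said is narrower: during treatment, its Device-use part has no planned objective record to draw on.

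The power figures deserve caution. The only adherence evidence in the documents is favourable. Benefits in the earlier trial arose at about 84% use, so an effect taken from it would already include that dilution. The same section reports gains that held or grew a month after treatment ended, which does not obviously fit a per-session effect. The planned analysis is ANCOVA, not a t-test. All of this stands, and it limits the figures to illustration.

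Finally, asking about missed sessions could prompt talk of sensations. That risk is small but not nil. It is contained because the coordinator who performs assessments takes no part in the interim calls.

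**Conclusion.** The point holds as a gap in trial conduct. No objective use data are planned to reach the site during the 12 weeks, and the scheduled calls list no question on sessions, so low use of a working Device may pass unnoticed while it could still be raised. The likely consequence is dilution towards no difference, not a false positive, and the log still allows use to be described afterwards. The size of any gain is unknown. The case for change rests on its low cost: the count is already on the display and the calls are already scheduled. It assumes that the counter falls only when a treatment is run, which the documents do not state.

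**What to change.** - When the prescription is loaded at the training visit, record the starting treatments-left count on the CRF. Have the sponsor confirm how the counter handles missed and aborted runs.
- At the week 3, 6 and 9 calls, ask the participant to read the treatments-left count from the display and enter it on the CRF with the date.
- Compare it with the starting count minus sessions due by the call date: 42, 84 and 126 at exactly 3, 6 and 9 weeks, otherwise two per elapsed day.
- Set in advance how far behind triggers action. The action is neutral encouragement and an offer of the telemedicine retraining already in the protocol.
- Keep the question to counts and practical obstacles, not sensations, and keep the counts from the assessing coordinator.
- Do not link the count to the withdrawal criterion.
- After Device return, check the recorded counts against the downloaded log.

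Cost: one CRF field at loading, one question and one field per call, about a minute each, with no new contacts. The downside is the small risk of unblinding talk reaching the calling coordinator, who does not perform assessments.

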Secondary Objectives: To test hypothesis that 12-weeks of BID tvCVS treatments increase functional connectivity in the brain.

Exploratory Objectives: This study will seek to establish the relationships between changes in cerebral perfusion and CVR with improvements in clinical endpoints and to evaluate whether these changes are durable (at an assessment five weeks after the cessation of treatments). Furthermore, the feasibility of detecting change in cerebrovascular reactivity (CVR) as assessed via transcranial Doppler sonography (TCD) will also be explored as well as pulse wave velocity (PWV).

Study Design

A double-blinded, randomized trial comparing two different neurostimulation patterns will explore the effects of tvCVS treatments on changes in biomarkers of neurovascular status (i.e. cerebral blood flow perfusion and cerebrovascular reactivity) as well as their relationship to clinical endpoints. Eligible and enrolled participants will be randomly allocated in a 1:1 ratio using block randomization by the clinical site. Participants will be trained in the clinic to self-administer device treatment and then will continue to self-administer the ~19-minute treatments twice daily for 12 weeks in the home. Individual stimulation sessions will be spaced a minimum of 1 hour apart. Outcome measures will be administered at the baseline, the end of the 12-week treatment period and at 5 weeks post-treatment. Study participants will continue to take their approved PD medications throughout the study and will maintain patterns of usage throughout.

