Participants will be screened for COVID-19 upon arrival to the clinic. Effort should be made to schedule the imaging visit within 24 hours of the virtual visit. On arrival, the MDS-UPDRS part III and the Timed Up and Go (TUG) will then be administered. The bilateral ear exam will be performed. Participants will then undergo the Magnetic Resonance Imaging (MRI) protocol and the transcranial Doppler sonography recordings of a hypercapnia challenge outlined above. Pulse wave velocity may be measured at the time of the transcranial Doppler sonography recordings. The PROs will be collected and checked for completeness. Participants will be asked to complete missing items or complete in full in the clinic if forms were left at home. Devices will be collected. The Inventory Control Log should be updated noting the return date of the Device. The Device should then be returned to Robling with a completed Device Return Form. **Should participants forget to bring their TNM™ Device to this visit, they will be provided with an addressed pre-paid FedEx box that can be used to ship the Device directly back to Robling. Coordinators should check tracking information and follow up with reminder phone calls to ensure return of the Device.

Follow up visit (remote) – week 17:

During this remote visit, the study coordinator will administer the NMSS, the MDS-UPDRS parts II and IV as well as the modified MDS-UPDRS part III. They will also administer the MoCA, the MRI safety screening. Participants will then be asked to complete the (PROs) including the Geriatric Depression Scale (GDS), the Parkinson's Anxiety Scale (PAS), the Epworth Sleepiness Scale (ESS) and the Functional Assessment of Chronic Illness Therapy – Fatigue (FACIT-F) and to bring them to their scheduled imaging visit.

Follow up visit (in clinic)- week 17, 1 day after remote visit:

Participants will be screened for COVID-19 upon arrival to the clinic. Effort should be made to schedule the imaging visit within 24 hours of the virtual visit. On arrival, the MDS-UPDRS part III and the Timed Up and Go (TUG) will then be administered. Participants will then undergo the Magnetic Resonance Imaging (MRI) protocol. A bilateral ear exam will only be performed if there were residual ear-related AEs at the last treatment visit.

SCHEDULE OF ACTIVITIES

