Packets containing 4 sealed envelopes with the printed bar codes for randomization assignments will be provided by the Device sponsor. Each batch will contain two stimulation 1 and two stimulation 2 assignments. The envelopes will be randomly shuffled by an agent not involved with the study. A given packet will be completed before the next packet is opened. The device-training coordinator will load the treatment onto the device, will record the device number allocated to the participant and will train the participant according to the training script provided (see Study Coordinator Quick Reference Guide). If the participant makes a comment about feeling warming or cooling sensations that may potentially unblind the study staff to treatment allocation, this information is not to be shared with other study staff including other coordinators, the principal investigator, Device sponsor CRA, data analysts or the study statistician. All assessments will be performed by a study coordinator that does not take part in the interim phone calls. Participants will be told that pain should not be associated with treatment, and if they do experience pain, that they should stop treatment and contact the coordinator immediately and/or seek medical attention if necessary. However, they will also be told that in the absence of pain, for the integrity of the trial, they should not discuss their treatment experience with anyone associated with the study (e.g. other research staff, their caregiver or other people they may know are participating in the trial). The exception being when they are specifically asked about their treatment experience in the Device Usability Questionnaire at the end of the treatment period.

Unblinding at the study site will only occur in the case of a SADE (serious adverse event at least possibly related to the device) or UADE (serious and unanticipated/unexpected adverse events at least possibly related to the device) that also requires cessation of device treatment. If this situation seems likely, the Unblinding Investigator, noted in the Delegation of Authority Log, should contact SNS to request approval to unblind. Upon receipt of written permission from the

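### The week-12 visit text does not fix who gives or handles the Device Usability Questionnaire, so the clinical rater could learn of treatment sensations before later exploratory ratings

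*Combined protocol and SAP*

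**What the plan says.** The section on the remote end-of-treatment visit (week 12) has the study coordinator give the NMSS, MDS-UPDRS parts II and IV and the modified part III. It continues: "They will also administer the MoCA, the MRI safety screening as well as a Device usability questionnaire". The following sentence has the participant complete a set of forms after the visit, including the GDS, PAS, ESS and FACIT-F, "and the Device Usability Questionnaire and to bring them to their scheduled imaging visit".

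Under Randomization, Blinding and Unblinding, participants who have no pain are asked not to discuss their treatment experience with anyone connected with the study. One exception is named: "The exception being when they are specifically asked about their treatment experience in the Device Usability Questionnaire at the end of the treatment period". The same section recognises the risk ("If the participant makes a comment about feeling warming or cooling sensations that may potentially unblind the study staff to treatment allocation") and answers it with a rule that "this information is not to be shared with other study staff including other coordinators". On the assessor it says: "All assessments will be performed by a study coordinator that does not take part in the interim phone calls".

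The week-12 clinic visit section places the full part III and the TUG on arrival, before imaging. Later in the visit, "The PROs will be collected and checked for completeness". No person is named for this, or for forms that are completed in the clinic. In Study Design, the fallback for participants who cannot attend has completed forms shown to the coordinator on video.

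**The concern.** A questionnaire that asks about treatment experience can carry the very information that the blinding section tries to contain. Stimulation 1 delivers warming to one ear and cooling to the other; stimulation 2 leaves the heating and cooling elements unpowered. The plan gives two routes for the questionnaire in adjacent sentences, and one of them runs through the person who rates the clinical scales. No rule keeps that person from asking it, collecting it or checking it.

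At stake are the clinical ratings made after the questionnaire. The Analysis Plan correlates imaging change with clinical change at both end of treatment and follow-up, so the week-17 ratings enter an analysis. The group-wise comparisons in that section do not say which endpoints they cover; if they include the clinical scales, a shift by an unblinded rater would enter the arm difference.

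**Working it through.** The plan gives no figure to reproduce. The check is a reading of the sections side by side, followed by a count of which ratings come after the questionnaire.

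1. **Mode.** The first week-12 sentence groups the questionnaire with the MoCA, which a rater conducts. The second groups it with self-completed forms. The verb does not decide between them, because Study Design uses it for every outcome, participant-completed forms included: "Outcome measures will be administered at the baseline, the end of the 12-week treatment period and at 5 weeks post-treatment". The mode is therefore not fixed.

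2. **Handler.** If the questionnaire counts as an assessment, the blinding section's sentence on assessments gives it to the rater. If it is a take-home form, the week-12 clinic section leaves the checker unnamed and the video fallback says only that it is the coordinator. Neither excludes the assessor.

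3. **Existing safeguards.**
   - The assessor is kept away from the interim calls; the questionnaire is not mentioned.
   - The no-sharing rule stops one person passing information to another. It protects the assessor only when someone else receives the answers.
   - Blinded analysis covers the analysts, not scores that have already been given.
   - Study Design allows part III to be videotaped for review, but does not require scoring by a rater who has not seen the questionnaire.

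4. **Ratings after the questionnaire.** Inputs are the rater-administered measures in the week-12 and week-17 visit sections, without the modified part III, which Study Design calls a backup.
   - Each time point: remote NMSS, parts II and IV, MoCA = 4; clinic part III and TUG = 2; total 4 + 2 = 6. Two time points: 2 × 6 = 12.
   - Rater asks the questions: 2 (week-12 clinic) + 6 (week 17) = 8 of 12, or 67%.
   - Self-completed, assessor handles the form: 0 + 6 = 6 of 12, or 50%. Week 12 is protected because part III and TUG come before form collection.
   - Self-completed, someone else handles the form: 0 of 12.

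5. **How firm the counts are.** Study Design lists MDS-UPDRS part I at all three time points, although the week-12 and week-17 visit text omits it. Adding it to the remote scales gives 7 per time point and 14 in all: 2 + 7 = 9 of 14, and 7 of 14. Leaving out the TUG, a timed test, gives 5 per time point and 10 in all: 1 + 5 = 6 of 10, and 5 of 10. The MoCA is also a test of performance, and the counts treat all scales alike. The week-12 remote scales are counted as unexposed because they are listed before the questionnaire, but that order is not mandated. The counts are approximate for these reasons: about two thirds in one case, about half in the other.

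**The case against.** The best reply is that the text, read as a whole, describes a take-home form. Study Design and the screening visit section set out one routine for participant forms: supplied beforehand, completed at the end of the virtual visit, brought to the clinic. The second week-12 sentence puts the questionnaire in that routine, and administering it may mean no more than issuing it. Week 12 is then safe, and the later check is for completeness, not a review of answers. Harm also needs a chain: the assessor sees the answers, the answers differ by arm, the assessor infers allocation, and the scores shift.

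Three further facts weaken the chain. Participants are not told that the device works through ear-probe temperature. The unpowered arm also feels some cooling at first, from room-temperature earpieces. The background section reports that participants' guesses in the earlier Parkinson's trial suggested effective blinding.

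Much of this stands, and it is why the point is minor. It does not remove the point. The first sentence still lists the questionnaire beside the MoCA as something the rater gives, and a completeness check puts the answers in front of whoever makes it. The earlier trial's guesses came from participants, not raters, and the documents do not show that its placebo matched stimulation 2.

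A reader might go further and infer that raters will be unblinded, or that the trial's main results are at risk. The documents do not support either. The questionnaire's items are not given, so what they reveal cannot be judged. The primary endpoints (perfusion and cerebrovascular reactivity) and the secondary endpoint (functional connectivity) are imaging measures, not coordinator ratings, and all endpoints are to be analysed blind.

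**Conclusion.** The point holds as a minor one with a cheap improvement. The plan gives two incompatible instructions for one questionnaire, and one of them, followed as written, can expose the rater before the week-12 clinic part III and TUG and before all week-17 ratings. On the self-completed reading, only the week-17 ratings are at risk, and only if the assessor handles the form.

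The size is an opportunity count only: about 8 of 12, about 6 of 12, or none, depending on the reading. It assumes that the remote week-12 scales come before the questionnaire, as listed. It may be tempting to put a figure on the bias in SD units or on a spurious correlation. The documents give nothing from which to derive one; any such figure would restate an assumed rater shift. A constant shift per arm would also leave within-arm correlations unchanged, and the Analysis Plan does not say whether the arms are pooled. What can be said is that only exploratory clinical ratings, and their correlations with imaging change, could be affected.

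**What to change.** Three changes of wording:

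1. In the remote week-12 visit section, remove the questionnaire from the list that the coordinator administers, and keep it among the self-completed forms.
2. In Study Design and the week-12 clinic visit section, state that a coordinator who is not the assessor collects and checks this form, after part III and TUG at week 12. Cover forms completed in the clinic and forms shown on the fallback video call.
3. In the blinding section, state that the assessor does not see the form or hear its answers until that participant's week-17 ratings are complete.

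No new role is needed, since the assessor must already be someone other than the coordinator who makes the interim calls. The cost is that the non-assessor coordinator must be available at each week-12 clinic visit or fallback call.

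The change does not close every route to the assessor. Adverse events are asked about at study visits by staff whom the plan does not separate from the assessor, and nothing bars the assessor from giving device training.
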